**Inclusion Criteria:** • Male 18 to 60 years old or female between 18 and 50 years old; • Self-report smoking ≥ 5 cigarettes/day for at least the past year; • Motivated to quit smoking (self-report ≥ 7 on 10-point Likert-type scale); • In stable physical/mental health; • Self report of regular menstrual cycles (female only) • Willing to use double-barrier contraception method if sexually active and not surgically sterilized; • English fluency; • Understand the study procedures and able to provide informed consent; • Ability to participate fully in research elements for the duration of the trial.

**Exclusion criteria:** • Current use of other types of tobacco, nicotine replacement therapy, or smoking cessation medications; • Current or recent (< 3 months) breastfeeding (females only); • Current or planned pregnancy within the next three months (females only); • DSM-IV diagnoses for psychotic disorders, bipolar disorder, ADHD, major depressive disorder within the last 3 months, • Substance dependence within the last 3 months with the exceptions of nicotine dependence and non-daily use of marijuana.; • Unstable psychotropic medications (< 3 months); • Current use of exogenous hormones, finasteride (propecia), efavirenz, red clover, ketoconazole and other drugs that are CYP3A4 inhibitors; • Conditions contraindicated to progesterone treatment (including, but not limited to, thrombophlebitis, deep vein thrombosis, pulmonary embolus, clotting or bleeding disorders, heart disease, diabetes, history of stroke, allergy to peanuts, hypersensitive to progesterone and liver dysfunction).

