#### B.4.6. Study Measures

**Prevalence of Relapse (Primary Outcome) and Days to Relapse (Secondary Outcomes):** We will assess smoking status using three methods (one based on self-report and two based on biochemical confirmations). *First*, at each clinic visit the TimeLine FollowBack (TLFB) method will be completed. The TLFB is a validated retrospective data capture technique (Sobell et al 1996). Marijuana users will complete an additional TLFB for marijuana use. *Second*, the first biochemical confirmation is expired air carbon monoxide (CO) measurement. The CO levels will be collected to each visit. Expired air CO sensitivity and specificity is approximately 90% (Jarvis et al 1987). Subjects will exhale into a CO monitoring device (Bedfont Scientific Limited Company), calibrated weekly to verify accuracy. For sample collection, subjects blow into a breathalyzer and analysis occurs immediately. CO levels > 5 ppm are indicative of acute smoking. *Third*, we will measure urinary cotinine, a major metabolite of nicotine and a biological indicator of nicotine exposure. A spot urine sample will be collected at the Week 4 and Week 12 clinic visits. The cotinine test has a sensitivity of 96-97% and a specificity of 90-100% (Jarvis et al 1987). A cotinine level of less than 15 ng/mL is indicative of abstinence (half-life of cotinine is 19-30 hours). Samples will be analyzed in batches at the Minneapolis Medical Research

Foundation Division of Toxicology using gas chromatography (Hewlett-Packard) in Year 5. The use of two different forms of biochemical confirmation of smoking status will eliminate potential false-positives that occur with using only one of these items.

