Days to relapse will be defined using continuous abstinence (CA), prolonged abstinence (PA) and point prevalence (PP) definitions (Hughes et al 2003). CA, a traditional measure, defines a single puff off a cigarette as relapse. The more liberal PA measure reflects sustained abstinence and defines relapse as seven consecutive slips (i.e., a puff or more) without a 24-hour period between any slip. The day of relapse is the first day of a slip. The CA and PA smoking outcomes will range from 0 (i.e. smoking on quit date) to 90 (i.e. not smoking at the end of the study). PP is a binary outcome of smoking relapse and is defined as a single puff off a cigarette during the seven days prior to a pre-specified time point of interest – Week 4 and Week 12. Week 4 prevalence of relapse is our primary outcome; week 12 prevalence of relapse is a secondary outcome. Self-report and biochemical measures will be combined to determine CA, PA, and PP.

Impulsivity Measures (Secondary Outcome): This P50 will examine “impulsivity” correlates broadly in rodents and humans across two substance use disorders (nicotine, cocaine-nicotine). Here we operationalize determination of impulsivity with several instruments.

Subjects will complete *three self-report measures* that have been computerized at each clinic visit beginning at Screening Visit 2. These measures will assess the characteristics of impulsivity, inhibition, planfulness, and cognitive impairments, key areas of focus in this grant.

- *Behavioral Inhibition/Activation scales (BIS/BAS):* These short 20 items forms commonly used scales to study externalizing tendencies (Carver and White, 1994). Investigators in Project II have used this instrument with success.
- *Barratt Impulsiveness Scale (BIS):* This item contains 30 item self-report measure self-control (Patton et al 1995). Doran and colleagues (2004) demonstrated that impulsivity, as measured with this item, was a predictor of smoking relapse.
- *Brief Self Control Scale (BSCS):* This item consists of 13 questions rated on a 4-point scale from “very true” to “very false” on items reflecting the ability to control problematic behaviors (Tangney et al 2004).

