- **Perceived Stress Scale** (PSS; Roberti et al, 2006): This ten item questionnaire will measure perceived stress. The items are rated on a 5-point scale, ranging from 0 (never) to 4 (very often), and they focus on events during the last week. The scale has adequate reliability and validity. This item will only be completed once during the screening process. This item will be completed at Screening Visit 1. This item will be completed at each clinic visit thereafter.
- **Life Event Occurrence Survey** (LEOS; McKee et al, 2005): This item will assess and account for the presence of current or recent significant life events. This measure includes 38 yes/no questions assessing various events that may have happened in the last six months including aspects of work, social life, family and finances. The measure includes instructions on how to rate the level of disruption the event caused in the subjects life from none too severe disruption. This measure will be administered at screening visit 1 and the final visit W12.
- **Columbia-Suicide Severity Rating Scale:** This questionnaire (C-SSRS; Posner et al, 2009) will be completed at each clinic visit to assess suicidal ideation, given this is listed as an SAE on the Prometrium label. If any item of suicidality is endorsed referrals to the appropriate mental health care will be made.
- **Sociodemographic Variables:** At the first screening visit we will collect information on age, race/ethnicity, education, income and other related variables. This item will be completed at Screening Visit 1 only.
- **Serum Estradiol:** At Screening Visit 1 and clinic visits 0-4, 8 and 12, blood samples will be collected to allow for the measurement of serum estradiol. Following identical procedures described above for serum progesterone, approximately two mL of serum will be analyzed by HealthEast Medical Laboratories using chemiluminescence.
- **Leisure Time Exercise Questionnaire** (LTEQ): This questionnaire has four-items to assess strenuous, moderate and mild exercise completed during leisure time and has high reliability ( $r=0.83, 0.85$ ; Gordin & Shepard, 1985).
- **Caffeine Use:** Caffeine use will be collected via self-report at each clinic visit using the TimeLine FollowBack methods in which participants will report the total number of ounces of caffeinated beverages drank per day for each day.

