## **SCOR P1 and MJ**

### **Rules/Changes**

**Last Updated: 9/8/16**

- In order to be eligible at BL, subject must be averaging 4.5 CPD for the past 2 weeks. If a subject is smoking less than 4.5 CPD, they will be dropped from the study and filed as "SCREEN FAIL" (1/1/15).
- Week 0 clinic visit must be completed on the subject's quit date. If this is not possible, it may be completed AFTER the quit date but a protocol deviation must be made. Week 0 cannot be completed BEFORE quit date (1/3/15).
- Subjects are allowed to miss 2 clinic visits over the entire study to eligible for the \$75 bonus at Week 12 – unless a cancellation was made by study staff (instead of the subject). That absence would NOT count against the bonus (1/29/15).
- ALT/AST levels must not be higher than double the normal range to be enrolled at SC. If levels are higher than double the normal range, the subject will be notified of the results, referred to PCP for follow-up and invited back in 4 weeks to re-test. If levels are high but within double the normal range, the subject may be enrolled per [name] approval. He/she will be tested again at Week 1 and as long as levels have not gone up, they will be allowed to continue in the study (1/29/15).
- The last available time to start a follow-up appointment will be 5:00pm (Week 4, 8, 12 – 4:30pm)
- We will only collect 2 urine samples at each visit (00 & 01) (4/7/15).
- Samples to be sent for analysis:

Hormones	BL	W4	W12	(Blood)
Cotinine		W4	W12	(Blood)
- BDI scores will be monitored weekly by study staff. If a subject scores  $\geq 20$  or endorsed suicidal thoughts (Question #9), staff will start an AE and continue to monitor scores. If score decreases and is  $< 14$  after three weeks with no suicidal thoughts, the AE may be closed.

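### The prolonged-abstinence relapse rule counts slips, not days, so a lapse of a day or two can qualify while one cigarette every 24 hours never does

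*Combined protocol and SAP*

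**What the plan says.** Section B.4.6 (Study Measures) gives two definitions for days to relapse. For continuous abstinence, "CA, a traditional measure, defines a single puff off a cigarette as relapse". For prolonged abstinence it states a purpose, "The more liberal PA measure reflects sustained abstinence", and then a rule: the measure "defines relapse as seven consecutive slips (i.e., a puff or more) without a 24-hour period between any slip". The date follows in the next sentence: "The day of relapse is the first day of a slip".

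The unit of the PA rule is the slip. Nowhere do the documents require smoking on several days, set a minimum time span, or say how to count several puffs or cigarettes on one day. The Outcome Measures section of the Data Safety and Monitoring Plan (DSMP) names PA without restating the rule.

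On data, B.4.6 says that "at each clinic visit the TimeLine FollowBack (TLFB) method will be completed" and gives no recording unit for smoking. On use, B.4.8 and the DSMP Data Analysis Plan run log-rank and Cox analyses of days to relapse separately for CA and PA under Hypothesis 2. They also use the days-to-relapse outcomes in the Cox models for Hypotheses 3 to 5, which they describe as hypothesis-generating.

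**The concern.** A prolonged-abstinence outcome is there to separate a brief lapse from a return to smoking. A count of slips with a gap limit does not do this reliably. It can be met in a short burst, because nothing requires the slips to fall on different days. It can be missed by steady light smoking, because a gap of 24 hours breaks the run. Both errors run against the stated purpose.

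The rule also asks whether any two successive slips were 24 hours apart, which needs a time for each slip. The documents describe no such collection.

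At stake is one of the two days-to-relapse versions under Hypothesis 2. Two competent programmers could build different PA datasets from the same records, and on some readings PA would add less to CA than the plan intends.

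**Working it through.** The plan states no figure that depends on the PA rule, so there is nothing to reproduce. The check applies the rule as written.

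**Inputs from the documents.** CA threshold: one puff. PA threshold: seven slips, no 24-hour gap. Smoking before the quit date: B.4.2 requires "Self-report smoking ≥ 5 cigarettes/day for at least the past year", and the rules list last updated 9/8/16 adds that at baseline the "subject must be averaging 4.5 CPD for the past 2 weeks". These describe smoking before the quit date, not during a lapse, and serve only as a reference level.

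**Step 1: time needed to meet the rule.** Assume each cigarette is one slip and *k* cigarettes a day are spread evenly over 16 waking hours (an assumption). Cigarette *j* of a day (*j* = 0, 1, …) is then smoked at 16*j*/*k* hours.

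- *k* = 7: the seventh slip comes at 6 × 16/7 = 13.7 h, on day one; largest gap 16/7 = 2.3 h. Rule met.
- *k* = 5: the seventh slip is the second on day two, at 24 + 16/5 = 27.2 h. Rule met.
- *k* = 4: 24 + 2 × 16/4 = 32 h. Rule met on day two.
- *k* = 3: 48 h. *k* = 2: 72 h. Rule met in both.
- *k* = 1: every gap is 24 h. Rule never met, however long the smoking lasts.

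If each puff is a slip, seven puffs suffice, possibly within one cigarette.

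**Step 2: overlap with CA.** This was simulated over 84 days with 1,500 subjects per scenario. None of the smoking assumptions comes from the documents: daily chance of starting a lapse 0.04; chance of smoking again the next day 0.5, 0.7 or 0.9; mean of 2, 3, 5 or 8 cigarettes per smoking day, at random times in 16 waking hours. Each cigarette is a slip, a gap of 24 h or more breaks the run, and relapse is dated to the start of the qualifying run. The contrast is a rule of seven consecutive smoking days. Entries are percentages of those who lapse, for continuation 0.5 / 0.7 / 0.9.

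| Mean per smoking day | As written: same day as CA | As written: any PA relapse | Seven days: same day as CA | Seven days: any PA relapse |
|---|---|---|---|---|
| 2 | 10.0 / 19.9 / 34.8 | 32.9 / 59.4 / 88.7 | 1.7 / 12.2 / 52.1 | 5.2 / 31.2 / 82.8 |
| 3 | 28.6 / 45.3 / 66.7 | 67.7 / 85.1 / 96.4 | 1.9 / 11.9 / 53.2 | 4.3 / 29.9 / 82.7 |
| 5 | 57.6 / 74.0 / 89.5 | 88.5 / 93.4 / 98.4 | 1.9 / 12.3 / 53.7 | 4.9 / 29.1 / 81.3 |
| 8 | 85.2 / 90.1 / 97.0 | 98.4 / 98.8 / 99.8 | 1.4 / 11.5 / 53.4 | 4.0 / 30.0 / 83.7 |

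As written, PA and CA fall on the same day in 10% to 97% of lapsers. The result depends heavily on cigarettes per smoking day, whereas the day-based rule hardly does. In one cell (2 per day, continuation 0.9) the day-based rule agrees with CA more often, 52.1% against 34.8%. There, gaps of 24 h or more interrupt the slip count even though smoking continues from day to day, which is the second fault in Step 1.

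**Step 3: can the data support the rule?** The timeline follow-back (TLFB) items differ in format. For caffeine, "participants will report the total number of ounces of caffeinated beverages drank per day for each day"; for marijuana, the number of days used since the last visit; for smoking, no unit is given. None of these describes recording the time of each slip.

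**The case against.** The strongest reply is that a slip defined as a puff or more is an occasion, so all the puffs of one cigarette are one slip. If smoking is recorded by day, the practical slip may even be a smoking day. Seven consecutive slips would then be close to seven consecutive smoking days, and the problem would largely disappear. That may be what was meant, and the paper cited for the definitions may say so. But the protocol writes its own rule, and that rule does not say it. The 24-hour clause also points to timing within and between days.

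Several stronger inferences are tempting, and the documents do not support them:

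- **That one day at the entry minimum is a PA relapse.** Five cigarettes are five slips. This follows only if each puff counts; by cigarette, the seventh slip falls on day two.
- **That PA is no more liberal than CA, or nearly duplicates it.** On any reading, every PA relapse is also a CA relapse and the reverse fails: isolated slips still separate them. The overlap depends on how lapsers smoke, which is not given.
- **That the smoking TLFB holds only daily totals.** This borrows from the caffeine item. The smoking format is not stated.
- **That PA takes the CA date by definition.** The dating sentence follows the PA rule directly, and its natural reading is the start of the qualifying run. Someone with two cigarettes on day 3, none until day 40 and daily smoking thereafter at a level that meets the rule would be dated day 40. The other reading, day 3, is possible only because the sentence does not name the slip.

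**Conclusion.** The point holds as a fault in the written rule, not only a missing detail. Counted by cigarette, the rule is met within one day at 7 per day and in about 27 hours at 5 per day, but never by cigarettes 24 hours or more apart. That does not fit a measure of sustained abstinence. The times rest on even spacing over 16 waking hours; the 10% to 97% overlap with CA rests on assumed smoking patterns and shows a direction, not a forecast.

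The reach is limited to the PA version of days to relapse: Hypothesis 2 and the exploratory Cox models. Hypothesis 2 is also addressed by CA days to relapse and week-12 relapse. The primary week-4 point-prevalence outcome and its power do not use the rule. The correction is worth making because the outcome is pre-specified and the change is small.

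**What to change.** Before unblinding, define PA relapse on the day scale in B.4.6. For example: any smoking (a puff or more) on each of seven consecutive days by TLFB, with the day of relapse equal to the first day of that qualifying run. Keep CA as the first day with any puff. If the sponsor intended a different unit or run length, state that instead, say how several occasions on one day are counted, and confirm that the data collected can support it. State the recording unit of the smoking TLFB in the same place.

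The cost is a sentence or two in B.4.6. If the smoking TLFB is recorded by day, the outcome can be derived from data already planned, with no new visits or measurements.

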- **Minnesota Nicotine Withdrawal Scale (MNWS; Hughes & Hatsukami, 1998):** This item includes measurement of: irritability, anger, anxiety, difficulty concentrating, restlessness, depressed or sad mood, and hunger. MNWS scores are calculated without the item of craving. We have changed the wording of the craving item to 'desire to smoke,' and its mean scores are analyzed separately in light of evidence suggesting distinct patterns of craving from other withdrawal symptoms (Hughes & Hatsukami 1998). This item will only be completed once during the screening process. This item will be completed at Screening Visit 1. This item will be completed at each clinic visit thereafter.
- **Questionnaire for Smoking Urges (QSU-brief; Cox et al. 2001):** This item is the shortened version of the QSU (Tiffany & Drobis, 1991) and will assess smoking urges. It includes 10 items clustered into two factors similar to those assessed by the longer version of QSU. Factor 1 includes items that indicate a strong desire and intention to smoke. Factor 2 includes items indicating expectation of a relief from negative affect with an urgent desire to smoke (Cox et al, 2001). This item will only be completed once during the screening process. This item will be completed at Screening Visit 1. This item will be

completed at each clinic visit thereafter.

- **Profile of Mood States** (POMS; McNair et al, 1971): On this 72-item form subjects use a 5-point Likert-type scale, to indicate 10 subscales (Evans et al 1998) including positive mood, arousal, vigor, elation, friendly, fatigue, tension-anxiety, depression-dejection, confusion, and anger-hostility. This item will only be completed once during the screening process. This item will be completed at Screening Visit 1. This item will be completed at each clinic visit thereafter.
- **Beck Depression Inventory-II** (BDI-II, Beck et al, 1996): This is the most commonly used screening measure for adults and will be used to assess depressive symptoms. This item will only be completed once during the screening process. This item will be completed at Screening Visit 1. This item will be completed at each clinic visit thereafter.

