Safety analyses: Adverse events will be quantified separately by sex and treatment groups and compared across treatment groups with Fisher's exact test (for binary events) or with chi-square test (for counts of events or event rates).

Secondary outcome analyses: These address Hypothesis 2. Our secondary outcomes include the binary indicator of relapsed yes/no at the week 12 visit, and days to relapse, as described above. The binary outcome will be analyzed as described for the primary outcome. Days to relapse will be analyzed using Kaplan-Meier

curves with a log-rank test comparing treatments (unadjusted) and Cox proportional hazards analysis (adjusted for other characteristics), both of which allow for loss-to-follow up via right censoring (Therneau and Grambsch, 2000), separately for the CA and PA definitions. Adjusting variables will be selected as described for the primary outcome. The proportional hazards assumption on the treatment effect will be examined and tested (Lin, Wei, and Ying, 1993; Grambsch and Therneau, 1994).

Other analyses: To address Hypothesis 3, we will pool the male and female data and test for an interaction between sex and treatment assignment in an adjusted Cox regression for the days to relapse outcomes. To address Hypothesis 4, we will test a baseline impulsivity by sex interaction in the logistic regressions for the binary outcomes and in the Cox regressions for the days to relapse outcomes. To address Hypothesis 5, we will test a baseline impulsivity by baseline serum progesterone interaction in the logistic regressions for the binary outcomes and in the Cox regressions for the days to relapse outcomes. While this study was designed to be powered for Hypothesis 1, rather than for these comparisons, these will be used to generate preliminary data and hypotheses for future research on sex differences in addiction treatment and impulsivity.

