Generic Prometrium, a natural progesterone, is generally well tolerated. The most common adverse effect is sedation. Other less common adverse effects include menstrual irregularity, spotting or breakthrough bleeding, dizziness, cramps, nausea, fatigue, headache and breast tenderness (de Lignieres, 1999; Simon, 1995, Sofuglu, 2009). Other side effects attributed to synthetic progesterone, including depression, fluid retention, pruritus, jaundice, rash and thrombotic disorders, are unlikely to occur. Recently there have been reports of increased risk of stroke, coronary artery disease, venous thromboembolism and breast cancer in postmenopausal females who have been on long-term hormone replacement treatment with estradiol and progestin (medroxyprogesterone) combination (Anonymous, 2002; Grady et al., 2002; Hulley et al., 2002; Nelson et al., 2002). While some of these adverse events develop after years of treatment, venous thromboembolism is seen within the first year of treatment (Anonymous, 2002). It is possible that progestins may contribute to thromboembolism seen during estradiol and progestin treatment and thromboembolism is listed in the PDR as one of the adverse events for medroxyprogesterone treatment (PDR, 2002). In contrast to synthetic progestins, natural progesterone is not known to cause thromboembolism (PDR, 2002). However, as a safety measure for these serious adverse events, we will exclude subjects with history of thrombophlebitis, deep vein thrombosis, pulmonary embolus, clotting or bleeding disorders, heart disease, diabetes or history of stroke. Possible adverse events from generic Prometrium will be assessed weekly by the research nurse ([name], NP) in consultation with the study physicians ([name] MD, [name] MD). If the side effects cannot be tolerated the medication dosage will be decreased to 200 mg daily.

Although uncomfortable, withdrawal symptoms do not pose significant health risks. Subjects who participate in this study will be asked to quit smoking on an assigned quit date. The smoking abstinence may result in increased irritability, anxiety, tension, depression, increased hunger or drowsiness.

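### No arm comparison is planned for the C-SSRS or for BDI-II scores or change, so a modest worsening of mood on progesterone would be detected with low power

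*Combined protocol and SAP*

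**What the plan says.** B.4.6 (Study Measures) says the C-SSRS "will be completed at each clinic visit to assess suicidal ideation, given this is listed as an SAE on the Prometrium label". The consequence it states is: "If any item of suicidality is endorsed referrals to the appropriate mental health care will be made". Of the BDI-II the same section says: "This is the most commonly used screening measure for adults and will be used to assess depressive symptoms". The BDI-II is given at Screening Visit 1 and at every clinic visit after that. Both instruments are listed under Other Covariates.

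B.4.8, Safety analyses, says: "Adverse events will be quantified separately by sex and treatment groups and compared across treatment groups with Fisher's exact test (for binary events"; a chi-square test is named for counts or rates. Section E of the Data Safety and Monitoring Plan (DSMP) repeats this and adds that a nurse or physician asks about and logs events at each visit. The Primary, Secondary, Other and missing-outcome paragraphs of B.4.8, and their DSMP counterparts, do not name the C-SSRS or the BDI-II.

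The link from the BDI-II to AEs is on the Rules/Changes page at the end of the document (last updated 9/8/16). It says "BDI scores will be monitored weekly by study staff" and opens an AE if the total is 20 or more "or endorsed suicidal thoughts (Question #9), staff will start an AE and continue to monitor scores". Neither trigger refers to the participant's earlier score.

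**The concern.** The instrument chosen because of a labelled risk has no arm comparison in the plan. The one collected most fully, the BDI-II, is reduced to a yes/no event that takes no account of where the participant started. Someone who moves from 4 to 18 is not an event on total score, while someone who enters at 20 or above and stays there is.

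The documents themselves make mood a question worth answering. DSMP section F lists depression among effects attributed to synthetic progesterone and calls these unlikely here. On quitting it says: "The smoking abstinence may result in increased irritability, anxiety, tension, depression, increased hunger or drowsiness". B.4.5 cites earlier progesterone use of under one month, and B.3 says chronic use as a cessation aid has not been studied. Twelve weeks of randomised mood data are therefore useful, and a non-significant Fisher test on these events would be weak reassurance.

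The two suicidality routes also differ. Question #9 of the BDI-II opens an AE; for an endorsed C-SSRS item only referral is stated.

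**Working it through.** **1. The plan's own power figure.** The documents state no power for mood or suicidality. The figure they do give (B.4.7) is 80% power at an odds ratio of 3.5, with 66% placebo relapse, 50 completers per arm within sex and two-sided alpha 0.025.
- PRO relapse odds = (0.66/0.34)/3.5 = 0.555, so p = 0.555/1.555 = 0.357, and the mean of the two proportions is 0.508.
- z = [0.303 - 2.241 × √(2 × 0.508 × 0.492/50)] / √((0.66 × 0.34 + 0.357 × 0.643)/50) = (0.303 - 0.224)/0.0953 = 0.83.
- Power = 79.7%. The stated figure is reproduced.

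**2. Inputs for the mood check.**
- From the documents: 125 enrolled per sex, 1:1 (about 62 per arm within sex, 125 per arm pooled); 13 weekly visits, Weeks 0 to 12; AE cut-off of 20; Fisher's test.
- Assumed: BDI-II mean/SD of 5/5, 7/6 or 10/8 with a gamma shape; latent visit-to-visit correlation 0.6; two-sided alpha 0.05 (none is stated for safety); full attendance; a uniform shift on PRO at every visit. Question #9 and clinician-logged events are not modelled. Both within-sex and pooled results are given because B.4.8 quantifies AEs by sex and arm but compares across arms.

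**3. Method.** Planned route: the proportion of each arm ever at 20 or more, compared by exact Fisher power. Alternative: ANCOVA of Week 4 BDI-II on arm and baseline, with SE = SD × √(1 - r²) × √(2/n) and power = Φ(shift/SE - 1.96).

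Worked case, 7/6 with a 3-point shift: ever at 20 or more is 22.0% on PBO and 32.4% on PRO, giving Fisher power of 20% at 62 per arm and 41% at 125. A latent correlation of 0.6 implies r of about 0.56 between observed scores, so at 62 per arm SE = 6 × 0.829 × 0.180 = 0.89, and 3/0.89 - 1.96 = 1.4, which is 92%.

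**4. Results, uniform 3-point shift.**

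| Assumed BDI-II | Fisher, 62/arm | Fisher, 125/arm | ANCOVA, 62/arm | ANCOVA, 125/arm |
|---|---|---|---|---|
| Gamma 5/5 | 13% | 28% | 98% | >99% |
| Gamma 7/6 | 20% | 41% | 92% | >99% |
| Gamma 10/8 | 22% | 41% | 72% | 95% |
| Log-normal (mean 7.3, SD 6.3), 25% drop-out, no shift at Week 12 | 13% | 21% | 84% | 98% |

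The last row uses the drop-out rate from B.4.7 and removes the shift after medication ends at Week 11.

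**5. Other sizes of effect (gamma models).**
- 2 points: Fisher 7-11% within sex and 13-19% pooled; ANCOVA 39-76% and 67-97%.
- 4 points: Fisher 24-39% and 51-68%; ANCOVA 92% or more and above 99%.
- 5 points: Fisher 42-57% and 76-87%. In the log-normal model with drop-out, pooled Fisher power is 63-84% at 5 to 6 points.
- Harm confined to a minority, pooled: 10% of PRO worsening by 15 points gives Fisher 11-27% and ANCOVA 37-61%; 20% worsening by 10 points gives 22-35% and 57-89%.
- Of participants with a sustained 5-point worsening, 74%, 59% and 36% never reach 20 for baseline means of 5, 7 and 10.

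**6. Suicidality.** If ideation occurred in 2% on PBO and 5% on PRO, pooled Fisher power would be 14%; at 2% against 10% it would be 70%.

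**The case against.** The strongest reply is that the safety net is wider than the cut-off. Question #9 opens an AE at any total score, so some suicidal thoughts do enter the arm comparison. Clinicians ask about events at every visit, so ideation seen on the C-SSRS may also be logged, and the data safety board can ask for more. All of this stands. A reader might infer that C-SSRS ideation is never recorded as an AE, but the text is silent on that and does not exclude it. None of these routes is a planned comparison of C-SSRS findings or BDI-II scores.

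Three other inferences are not supported:
- That mood is measured because of the label. That reason is attached only to the C-SSRS; the BDI-II is there to assess depressive symptoms.
- That a real worsening would usually be missed. The documents give no BDI-II mean, SD, correlation or expected change, and pooled Fisher power exceeds one half from about 4 points in the gamma models.
- That entry symptoms and withdrawal bias the AE comparison. Both arms are randomised and both quit, so these add noise and are balanced in expectation.

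It is also fair to say that tabulating the C-SSRS brings no power for rare ideation. Its value is that the labelled risk is reported by arm.

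**Conclusion.** The gap is established from the text: there is no arm comparison of the C-SSRS, none of BDI-II scores or change, and a BDI-II route into the AE comparison that ignores baseline. Its consequence is low power for modest mood worsening. For a uniform 3-point shift, Fisher has about 13-22% power within sex and 21-41% pooled, against about 72-98% and 95-100% for a baseline-adjusted comparison of scores already collected. Pooled shifts of 5 points or more would usually be seen by either method.

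Every power figure for mood depends on assumed BDI-II inputs and leaves out Question #9 and clinician-logged events. The direction, with the score comparison ahead of the cut-off, was the same in every scenario tried, including harm confined to a minority. The point merits a change to the analysis section; it does not show that the trial's safety monitoring fails.

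**What to change.** Add to Safety analyses in B.4.8 and to DSMP section E:
- **C-SSRS.** Number and percentage, by sex and arm, with ideation or behaviour after first dose that was not present before first dose, as a descriptive table.
- **BDI-II.** A baseline-adjusted comparison by arm within sex (ANCOVA, or a repeated-measures model on the weekly scores), using the last available pre-dose score and otherwise Screening Visit 1. The later score is preferable because the delay from screening to dosing varies and screening falls on cycle days 1-7 in females.

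Baseline status may be shown descriptively beside BDI-triggered AEs, but no AE should be excluded on that ground. In the log-normal model with drop-out such a filter left Fisher power unchanged (13% to 12% within sex, 21% to 22% pooled), and it could hide worsening in participants who enter with high scores.

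B.4.6 and the Rules/Changes page should be reconciled on whether a positive C-SSRS is recorded as an AE.

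The cost is a few tables and models on data already collected, and some added safety comparisons to be read as exploratory. Monitoring and referral are unchanged.
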